## SUMMARY & OUTCOME OF CHANGES:

STUDY NUMBER	D-FR-52120-236		
AMENDED PROTOCOL VERSION NUMBER & DATE	Protocol Version 6.0: 08 October 2020		
SUBSTANTIAL 	NON-SUBSTANTIAL 		
REASON(S) FOR CHANGES	
The protocol was updated to:
 
 
Reflect that during Stage 2, two optimally safe and effective doses of Dysport will be further investigated; the option of testing one Dysport dose during Stage 2 was removed.
 
Clarify that the role of the DRC was to make recommendation on dose escalation, dose de-escalation, progression from Stage 1 to Stage 2 or study termination decisions in Stage 1.
 
Clarify in inclusion criteria 12b, the specific cohorts that enrolled subjects with primary vulvodynia versus secondary vulvodynia.
 
Shift the evaluation of CGI-C and PGI-C from secondary objectives/efficacy parameters to exploratory objectives/efficacy parameters.
 
Add guidance on COVID-19 infection to be reported as an SAE, and its impact on IMP administration.
 
Add a provision for the subjects to have their study visit assessments performed remotely, if they are unable to attend the site visit due to the COVID-19 pandemic.
 
Add permitted pain rescue medication during Stage 2.
 
Add further clarification in the statistical section on the: 
 
➢ Doses being evaluated in Stage 2,
 
➢ COVID-19 specific analyses,
 
➢ Intermediate analyses to be performed at the point when the DRC recommends moving to Stage 2 and
 
➢ Potential sample size recalculation for Stage 2 following the intermediate analysis.
 
 
 
Update the mFSFI questionnaire to version 1.3.
 
		
OTHER ACTION REQUIRED?	CRF UPDATE	Yes  No 	(tick one)
	LOCAL CONSENT FORM UPDATE	Yes  No 	(tick one)
	DATABASE UPDATE	Yes  No 	(tick one)
	STATISTICAL ANALYSIS PLAN (SAP) UPDATE	Yes  No 	(tick one)

1 INFORMATION TAKEN FROM THE PROTOCOL

1.1 Study objectives

1.1.1 Primary objective

Stage 1

The primary objective of the study is to assess the safety of increasing doses of Dysport in vulvodynia subjects with provoked vestibulodynia (PWD).

Stage 2

The primary objective of the study was to assess the efficacy of Dysport compared to placebo in vulvodynia subjects with PVD. However, the study was terminated before Stage 2 begins (please refer to Section 1.3.5).

1.1.2 Secondary objectives

The secondary objectives of the study are as follows:

Stage 1

- To assess the efficacy of increasing doses of Dysport compared to placebo in vulvodynia subjects with PVD
- To determine the doses of Dysport to be administered in Stage 2
- To assess the sensitivity of the endpoints used in Stage 1

Stage 2

- To define the optimal doses of Dysport with an acceptable benefit/risk profile for the treatment of vulvodynia with PVD
- To assess effect of Dysport on:
 - Vulvar pain
 - Use of pain rescue medication (type, dose and frequency)
- To determine if primary and secondary PVD subjects benefit from Dysport administration
- To assess the time to retreatment
- To assess the safety of Dysport

1.1.3 Exploratory objectives

The exploratory objectives of the study are as follows:

- To assess effect of Dysport on:
 - Clinical Global Impression (CGI) of the treatment effect (assessed by the investigator)
 - Patient Global Impression of severity of the pain (PGI-S) and Patient Global Impression of change in pain (PGI-C)
- Emotional response, cognitive response and associated life interference as assessed on modified Vulvar Pain Assessment Questionnaire (mVPAQ) subscales
- Sexual function
- To assess the efficacy of Dysport on the pelvic floor muscles pressure
- To assess the efficacy of Dysport on depression
- To assess the efficacy of Dysport on the quality of life

1.2 Study design

This is a Phase II multicentre, double-blind (DB), randomized, placebo-controlled, dose finding study to define the optimal doses of Dysport and evaluate its efficacy and safety compared to placebo in vulvodynia patients with PVD. Study treatment was injected at 5 needle insertion points at 10 injection sites in the vestibular area. The study consisted of a dose escalation stage (Stage 1) and a dose expansion stage (Stage 2). The purpose of the dose escalation was to determine the Dysport doses to be further investigated in Stage 2. Both Stage 1 and Stage 2 consisted of a DB period (treatment cycle 1; Dysport or placebo) followed by an open-label (OL) treatment period (treatment cycles 2 to 4; all subjects receive Dysport).

However, the study was terminated before Stage 2 begins (please refer to Section 1.3.5).

1.3 Methods and procedures

1.3.1 *Schedule of assessments*

The schedule of procedures and assessments during the study is presented in section 5.1 of the protocol.

1.3.2 *Planned sample size*

In Stage 1, the expected sample size was 10 evaluable subjects for PVD2 (secondary PVD subjects, i.e. having a past history of pain free intercourse or insertion of any object >1 cm diameter) cohort to be randomized and treated in a 4:1 allocation ratio (Dysport or Placebo) and 8 evaluable subjects for PVD1 (primary PVD subjects, i.e. having life-long PVD) cohort 4 treated in a 3:1 allocation ratio (Dysport or Placebo). After Cohort 3 (PWD2) and Cohort 4 (PWD1), the expected sample size was 10 evaluable subjects for additional PVD1 and PVD2 cohorts and treated in a 4:1 allocation ratio (Dysport or Placebo).

Subjects who discontinue prior to Week 6 for reasons unrelated to safety may be replaced at the discretion of the investigator and sponsor. As this is an exploratory stage, no formal power was performed. However, with 8 active subjects per PVD2 dose cohort and if there are 0 dose limiting events (DLEs) in a cohort, there is at least 80% probability that the true incidence of DLEs at the corresponding dose will not be greater than 18%. With 16 active subjects in PVD1 and PVD2 dose cohorts and if there are 0 DLEs in a cohort, there is at least 80% probability that the true incidence of DLEs at the corresponding dose will not be greater than 9%.

1.3.3 *Method of Randomisation*

In stage 1, for the PVD2 cohorts, subjects were randomised with a 4:1 (Dysport: placebo) ratio. For the first PVD1 cohort, subjects were randomised with a 3:1 (Dysport: placebo) ratio for Dysport 400 U and then for further PVD1 cohorts, subjects were randomised at 4:1 for Dysport 500 U and up to a maximum of 800 U. In an event, when the last subject in a cohort was being randomised, if an additional subject had been screened, this subject may be accepted in the cohort and be randomised.

1.3.4 ***Validation scale study D-FR-52120-252***

The psychometric properties of the dilator-induced pain Numeric Rating Scale (NRS), dilator size 6 insertion pain NRS, pain on intercourse NRS, mVPAQ, and modified Female Sexual Function Index (mFSFI) were to be evaluated using data collected from all subjects randomized in Stage 1 and Stage 2. The planned analyses of these data are described in the Psychometric Analysis Plan of validation study D-FR-52120-252. However, these analyses were cancelled following the decision to prematurely terminate the study.

1.3.5 ***Data review Committee and planned Analyses***

Data Review Committee

A DRC has been established to make recommendations for dose escalation and dose de-escalation or study termination decisions in Stage 1. It was planned that (a) if no subject reports a clinically significant AE (defined in the protocol section 3.1.1.1) in a cohort, the DRC will meet once all PVD2 and PVD1 evaluable subjects of a dose level have reached Week 6 to review the unblinded efficacy and safety data and decide the dose for the next cohort or proceed to Stage 2; (b) If any subject reports a clinically significant AE, then further enrolment into the cohort as well as retreatment in open label cycles at the current dose will be suspended and an ad hoc DRC meeting will be scheduled to review the data and make a recommendation with regards to further conduct of the cohort and of Stage 1.

Details related to DRC membership, responsibilities, procedures, role and remit are described in the DRC charter.

Early Study Termination Decision

Following the DRC meeting organized to review safety and efficacy data of cohorts 1 to 6 on the 16 OCT 2020, the DRC sent the following recommendation:

"No safety concerns noted in review of all available data. Efficacy cannot be assessed due to the small sample size of cohorts. The DRC would recommend that Stage 1 is not used to make an efficacy assessment, therefore there is no justification to increase the dose, nor to move to Stage 2."

Ipsen subsequently decided to close the study early and to run the final analysis based on available Stage 1 data. Subjects in the study are followed until 12 weeks after the last dose as described in the protocol section 3.9.

Final Analysis

The final analysis will be carried out once all subjects from cohorts 1 to 6 have completed end of study evaluation, after the database lock. All unblinded safety and efficacy data available at the time of the database lock will be analysed.

No control of the overall type I error rate is planned as only exploratory descriptive statistics are planned.

2 **SUBJECT POPULATIONS (ANALYSIS SETS)**

Screened population

The screened population is all subjects screened (i.e. who signed the informed consent).

Randomized population

Randomized population is all subjects randomized (i.e. who were randomly allocated to a treatment group).

modified Intent-To-Treat population

The modified Intent-to-Treat (mITT) population is all randomized subjects who received at least one IMP administration and had data for the vaginal dilator induced pain as reported on an 11-point NRS [using the Dilator Maximum Tested Size (DMTS) reported at Baseline] at Baseline and Cycle 1-Week 6 visit (i.e. at least one pain score for one dilator size, which enables an imputed pain score of 10 at DMTS if needed).

The mITT population will be analyzed using subjects as randomized.

Active Treatment Population

The Active Treatment Population is all randomized subjects who received at least one dose of Dysport (including only partial administration) during the DB and/or OL period.

Safety

The safety population is all randomized subjects who received at least one dose of IMP administration (including only partial administration).

The safety population will be analyzed using subjects as treated (i.e. according to actual treatment received).

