**Sample Size and Power Considerations:**

Stage 1: With 8 evaluable subjects on active treatment per PVD2 dose cohort and if there are 0 DLEs in a cohort, there is at least 80% probability that the true incidence of DLEs at the corresponding dose will not be greater than 18%. With 16 evaluable subjects on active treatment in PVD2 and PVD1 dose cohorts, and if there are 0 DLEs in the two cohorts, there is at least 80% probability that the true DLEs at the corresponding dose will not be greater than 9%. The ability to confidently rule out smaller true DLE incidence at a dose level will come from observations on subjects in Stage 2.

Stage 2: The study sample size required to have at least 80% power to detect a 2-point improvement between Dysport and the placebo group on mean change from baseline to Week 6 in the vaginal dilator induced pain as reported on a numeric pain rating scale (using the DMTS), assuming a common standard deviation of 3-point and using a one-sided 0.10 level test is 21 subjects per arm.

At the end of Stage 2, if the true DLE rate is 6% or greater, there is at least 80% probability to observe at least 1 DLE in 29 subjects (8 in Stage 1 and 21 in Stage 2). Therefore, if there are no observed DLEs in both Stage 1 and Stage 2 at a dose level, then there is good confidence that the true DLE rate is no more than 6%. If the dose chosen in Stage 2 has been tested on two cohorts (PWD1 and PWD2) in Stage 1, at the end of Stage 2, if the true DLE rate is 5% or greater, there is at least 80% probability to observe at least one DLE in 37 subjects (16 in Stage 1 and 21 in Stage 2). Therefore, if there are no observed DLEs in both Stage 1 and Stage 2 at a dose level, then there is good confidence that the true DLE rate is no more than 5%.

Following the review of data available from Stage 1, the sample size may be formally recalculated for Stage 2 after the intermediate analysis.

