## 11.2 Sample Size Determination

### Stage 1:

In Stage 1, the expected sample size is 10 evaluable subjects for PVD2 cohorts who will be randomised and treated in a 4:1 allocation ratio (Dysport or Placebo), and 8 evaluable subjects for PVD1 Cohort 4 treated in a 3:1 allocation ratio (Dysport or Placebo).

After Cohort 3 (PWD2) and Cohort 4 (PWD1), the expected sample size is 10 evaluable subjects for additional PVD1 and PVD2 cohorts and treated in a 4:1 allocation ratio (Dysport or Placebo).

Subject who discontinue prior to Week 6 for reasons unrelated to safety may be replaced at the discretion of the investigator and sponsor. As this is an exploratory stage, no formal power could be performed. However, with 8 active subjects per PVD2 dose cohort and if there are 0 DLEs in a cohort, there is at least 80% probability that the true incidence of DLEs at the corresponding dose will not be greater than 18%. With 16 active subjects in PVD1 and PVD2 dose cohorts and if there are 0 DLEs in a cohort, there is at least 80% probability that the true incidence of DLEs at the corresponding dose will not be greater than 9%. The ability to rule out smaller DLE rates with high confidence will come from observing additional subjects in Stage 2.

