### Stage 2:

The study sample size required to have at least 80% power to detect a 2-point improvement for an experimental drug arm relative to placebo on mean change from baseline to Week 6 in the vaginal dilator induced pain as reported on a numeric pain rating scale (using the DMTS) using a one-sided 0.10 level test (not corrected for multiplicity) is 21 evaluable subjects per arm (i.e. a total of 63 subjects). The following assumptions were used for the power statement:

- Expected outcome on the mean change from baseline to Week 6 in the vaginal dilator induced pain as reported on a numeric pain rating scale in the placebo group = 2-point decrease (reference approximated by VAS per speculum in Bornstein, 2010 [26])
- Expected outcome on the mean change from baseline to Week 6 in the vaginal dilator induced pain as reported on a numeric pain rating scale in a Dysport treated group = 4-point decrease
- Expected common standard deviation of the mean change from baseline to Week 6 in the vaginal dilator induced pain as reported on a numeric pain rating scale = 3-points (approximated per VAS data in Table 2 in Davis 2013 [27]).

Subject who discontinue prior to Week 6 for reasons unrelated to safety will be replaced at the discretion of the investigator and sponsor.

At the end of Stage 2, if the true DLE rate is 6% or greater, there is at least 80% probability to observe at least 1 DLE in 29 subjects (8 in Stage 1 and 21 in Stage 2). Therefore, if there are no observed DLEs in both Stage 1 and Stage 2 at a dose level, then there is good confidence that the true DLE rate is no more than 6%. If the dose chosen in Stage 2 has been tested on two cohorts (PWD1 and PWD2) in Stage 1, at the end of Stage 2, if the true DLE rate is 5% or greater, there is at least 80% probability to observe at least one DLE in 37 subjects (16 in Stage 1 and 21 in Stage 2). Therefore, if there are no observed DLEs in both Stage 1 and Stage 2 at a dose level, then there is good confidence that the true DLE rate is no more than 5%. If it is reasonable to assume that the relationship between toxicity and dose level is monotonic non-decreasing, then we may pool dose levels to obtain a higher degree of confidence for the lower dose level.

Following the review of data available from Stage 1, the sample size may be formally recalculated for Stage 2 after the intermediate analysis.

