3 STATISTICAL METHODS

3.1 Statistical analysis strategy

The statistical analyses will be performed in accordance with the ICH E9 guideline and will be based on the pooled data from the individual study sites, unless otherwise stated.

Medpace will perform the statistical analysis of the efficacy, safety, and antibodies data.

Overall, the analysis strategy is to evaluate safety and efficacy of Dysport compared to Placebo after single administration (DB period), and to evaluate efficacy and safety over repeated Dysport treatments, using analyses by Active Treatment Cycle.

Listings will be presented by subject for DB and OL periods together while the tables associated with the DB period will be separated from the tables assessing repeat treatment with Dysport.

Only descriptive statistics of Stage 1 data will be provided.

Double-Blind Period (Stage 1 Cycle 1) Analyses

For the analysis of the DB period, tables will be displayed using the following treatment group (DB treatment group) labels, in the following order:

- Placebo: placebo groups from all cohorts will be pooled, including for mVPAQ pain, mVPAQ life interference and mFSFI pain domain of cohort 1 despite the change in recall period and time of assessments (see protocol version 3.0).
- Dysport
 - Groups by dose (Dysport 100U, 300U, 400U, 500U, etc.)
 - All Dysport

[figure not shown]
Note: Cohort 1 (100U), 2 (300U), 3 (400U) and 5 (500U) included PVD2 subjects only. Cohort 4 (400U) and 6 (500U) included PVD1 subjects only.

Repeat treatment: Active Treatment Analyses

To assess efficacy and safety data over repeat treatments, data will be analysed using the Active Treatment Cycle approach as described in [Figure 1](#) below. These analyses will be performed on the Active Treatment population:

- for subjects treated with Dysport in the DB period, the first cycle in the DB period will be the first Active Treatment Cycle.
- for subjects treated with placebo in the DB period, the first cycle in the OL period will be the first Active Treatment Cycle.

[Figure 1](#) Active Treatment Cycle Analysis

Three types of summary tables will be produced:

- Summary by number of active treatment cycles: these tables will present the long-term efficacy and safety data with all doses combined, and will display subjects with at least 1 (2, 3 and 4) active treatment cycles.
- Summary by dose received at each active treatment cycle: to evaluate the safety of each dose at a given cycle.

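### Zero DLEs in 16 active subjects does not give 80% assurance of a true DLE rate of 9% or less on the exact binomial: it gives 77.9%, with an 80% upper bound of 9.6%

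*SAP*

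**What the plan says.** SAP 1.3.2 (Planned sample size) makes two statements about Stage 1.

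- One PVD2 cohort: "with 8 active subjects per PVD2 dose cohort and if there are 0 dose limiting events (DLEs) in a cohort", then "there is at least 80% probability that the true incidence of DLEs at the corresponding dose will not be greater than 18" percent.
- A PVD2 and a PVD1 cohort at the same dose, 16 active subjects, no DLEs: "there is at least 80% probability that the true incidence of DLEs at the corresponding dose will not be greater than 9" percent.

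Both come from the protocol. Section 11.2, Stage 1, opens the second one with "With 16 active subjects in PVD1 and PVD2 dose cohorts and if there are 0 DLEs in a cohort". The synopsis (Sample Size and Power Considerations) opens it with "With 16 evaluable subjects on active treatment in PVD2 and PVD1 dose cohorts, and if there are 0 DLEs in the two cohorts" and concludes "there is at least 80% probability that the true DLEs at the corresponding dose will not be greater than 9" percent. No interval method, confidence bound or prior is named in any of the three places.

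The Stage 2 text in protocol 11.2 makes parallel DLE statements in binomial terms, for example "if the true DLE rate is 6% or greater, there is at least 80% probability to observe at least 1 DLE in 29 subjects". It makes the same kind of claim for 37 subjects at a 5% rate.

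**The concern.** The 18% and 9% limits look as if they come from one calculation, with the limit halved when the sample doubles. The zero-event binomial bound does not quite halve in that way, so the 9% needed checking. If it is too low, the plan overstates how high a DLE rate a clean 16-subject dose level would rule out, in the stage whose primary objective is safety. The later tightening of the bound with Stage 2 subjects will not happen, because the study was terminated before Stage 2 began (SAP 1.3.5 and 5.1.2). The Stage 1 figures are therefore the only stated DLE precision that bears on the data collected.

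There is also a wording difference. The SAP and protocol 11.2 make the 16-subject figure conditional on no DLEs in a single cohort, whereas the synopsis requires none in both. A bound that uses all 16 subjects needs zero events in all 16.

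**Working it through.** **Inputs.** 16 active subjects, 0 DLEs, limit 9%; 8 active subjects, 0 DLEs, limit 18%; target 80% (all SAP 1.3.2). For comparison: 29 subjects at 6% and 37 at 5% (protocol 11.2, Stage 2).

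**Formulas (exact binomial, zero events).** Probability of at least one DLE in n subjects at true rate p: 1 − (1 − p)^n. One-sided 80% upper bound after 0 DLEs in n: 1 − 0.2^(1/n).

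**Does this formula fit the document's other statements?**

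- 29 at 6%: 1 − 0.94^29 = 0.834. Meets 80%.
- 37 at 5%: 1 − 0.95^37 = 0.850. Meets 80%.
- 8 at 18%: 1 − 0.82^8 = 0.796; bound 1 − 0.2^(1/8) = 0.182. Strictly below 80%, but the bound rounds to the stated 18%.

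**The 16-subject statement.**

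- At 9%: 1 − 0.91^16 = 0.779, which is 2.1 percentage points short.
- Bound: 1 − 0.2^(1/16) = 0.0957, or 9.6%, which rounds to 10% and not to 9%.
- At 10%: 1 − 0.90^16 = 0.815. For 8 subjects at 19%: 1 − 0.81^8 = 0.815.
- Sample needed for 80% at 9%: n = 17 gives 1 − 0.91^17 = 0.799, so 18 are needed.

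**Other methods, since none is named.** The posterior after 0 events in n is Beta(1, n + 1) with a uniform prior and Beta(0.5, n + 0.5) with a Jeffreys prior.

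| Method | n = 16: at 9% | n = 16: 80% bound | n = 8: at 18% | n = 8: 80% bound |
|---|---|---|---|---|
| Exact binomial | 77.9% | 9.6% | 79.6% | 18.2% |
| Poisson | 76.3% | 10.1% | 76.3% | 20.1% |
| Uniform prior | 79.9% | 9.0% | 83.2% | 16.4% |
| Jeffreys prior | 92.0% | 4.9% | 93.0% | 9.5% |
| Mid-P | 88.9% | 5.6% | 89.8% | 10.8% |
| Wilson | – | 4.2% | – | 8.1% |

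No row returns both 18% and 9% as its 80% bounds. The 9% may simply be 18% divided by two, but that is an inference.

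**Where 16 applies.** Both cohorts have 8 active subjects only from 500 U upwards. At 400 U the plan was 8 + 6 = 14 active, for which the bound is 1 − 0.2^(1/14) = 10.9%. Enrolment ended with Cohort 6. Cohorts 3 and 4 were at 400 U and Cohorts 5 and 6 at 500 U (SAP 3.1: "Cohort 4 (400U) and 6 (500U) included PVD1 subjects only"), so 500 U is the only enrolled dose level planned with 16.

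**The case against.** The strongest reply is that the sentence, read literally, is a probability about the true rate, which is a posterior statement, and that the exact binomial is carried over from differently worded Stage 2 text. With a uniform prior the result is 79.9% for 16 subjects and 83.2% for 8. If 79.6% is excused as rounding for 8 subjects, 79.9% should be excused for 16. Jeffreys, mid-P and Wilson readings satisfy both statements outright. Nor do the documents claim that 18% and 9% are themselves the 80% bounds, only that the probability is at least 80%. The Stage 2 limits of 6% and 5% also lie above their own exact bounds of 5.4% and 4.3%.

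Much of this stands. The error is not independent of method, and failing to return both limits as bounds says something about where the figures came from, not whether the sentence is true. It does not rescue the text as written. No prior is stated, the uniform prior still falls just short of 80%, and the only method the document's own wording points to is the binomial. That comparison with Stage 2 also shows limits rounded upwards there, as a claim of at least 80% requires; the 9% is rounded downwards.

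It is also true that nothing depends on the figure. Stage 1 is descriptive, DRC meetings are triggered by clinically significant AEs and by Week 6 completion, and SAP section 1 restates protocol text. Finally, replacement subjects and an extra randomised subject per cohort are allowed, so the treated number at 500 U may not be exactly 16. These points limit the importance of the error without removing it.

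**Conclusion.** The concern holds and is minor. On the zero-event exact binomial, 16 active subjects without a DLE give 77.9% at a 9% rate, and the 80% upper bound is 9.6%. The 8-subject statement is off by rounding only (79.6%, bound 18.2%). The arithmetic is certain. Calling it an error rests on reading Stage 1 with the formula that the Stage 2 wording implies; with a uniform prior the shortfall shrinks to 0.1 percentage point, and with a Jeffreys prior it disappears. The practical consequence is a slightly favourable safety-precision figure, stated in three places, which matters only if the study report carries it forward.

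**What to change.** Add a short correction note to the SAP or the study report that does the following:

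- names the method (exact binomial, zero events, one-sided 80% bound);
- gives 9.6% for 16 active subjects with no DLEs in the two cohorts together, and 18.2% for 8 active subjects with no DLEs; or, if whole numbers with at least 80% are preferred, 10% and 19% (81.5% each);
- optionally, says that the 16-subject figure does not apply to 400 U, where 14 active subjects were planned (bound 10.9%).

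If the report quotes a bound for a dose level with no DLEs, it should put the number actually treated into the same formula. The cost is one or two sentences and slightly less favourable figures. No protocol amendment or new analysis is needed, and no escalation rule or conclusion changes.
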